2. ASA IV
3. Patients who are known or suspected to be allergic to lidocaine.
4. Patients who are currently pregnant or breastfeeding.
5. According to the Summary of Lidocaine Product Characteristics, patients who may experience adverse reactions due to accumulation of lidocaine intravenous infusion.
6. The current liver function is abnormal, with ALT or AST exceeding the laboratory reference range by 2 times.
7. Currently severe renal insufficiency (blood creatinine $\geq 451\text{umol/L}$ or glomerular filtration rate (calculated by MDRD formula) $<30\text{ml/min}$).
8. Epilepsy.
9. Cardiac conduction abnormalities, including second or third degree heart block without a pacemaker, left bundle branch block, sick sinus syndrome, and pre excitation syndrome (confirmed by

electrocardiogram based on medical history), as well as patients in a low cardiac output state with currently reduced left ventricular ejection fraction.

10. Concurrent use with continuous infusion of other local anesthetics (such as epidural).
11. Patients who use drugs that may cause exclusion reasons, including Class I and III antiarrhythmic drugs (such as metoprolol, amiodarone), cimetidine, and antiviral drugs. Qualifications will be determined by local clinical doctors and verified by clinical trial doctors.
12. Patients weighing less than 40kg

Termination criteria for the study (subjects experiencing conditions that make it inappropriate to continue the study, including worsening of the condition, serious adverse events, poor compliance, etc.)

Research methods

1. Intervention measures

Research drug (IMP)

2% lidocaine hydrochloride injection for infusion, prepared as a 50mL syringe and continuously pumped for administration.

Placebo

0.9% sodium chloride solution for infusion, prepared into a 50mL syringe and continuously pumped for administration.

2. Dose plan

Lidocaine is administered intravenously at an ideal body weight (IBW) of 1.5 mg/kg starting from anesthesia induction, for 10-20 minutes, and then continuously infused at 1-1.5 mg/kg/h until 12 hours after returning to the ward, with a maximum rate of 120 mg/h. Use ideal weight instead of actual weight to prevent toxicity in very overweight patients. In patients with a weight lower than the ideal weight, the actual weight should be used to calculate the dose. The patient needs to be admitted to a highly dependent ward or equivalent facility for continuous cardiac monitoring during lidocaine infusion. Patients in the placebo group had the same infusion rate as those in the treatment group.

Example

IBW (Kg) initial dose (1.5 mg/kg) infusion rate (1.5 mg/kg/h)

40 3ml (10-20min) 1-3ml/h

50 3.75ml (10-20min) 1.25-3.75 ml/h

60 4.5ml (10-20min) 1.5-4.5 ml/h

70 5.25ml (10-20min) 1.75-5.25 ml/h

80 and above 6 ml (20 minutes) 2-6 ml/h

Table 1: Dose Guidelines Based on IBW (Broca Index): Male: Height (cm) -100; Female: Height (cm) -105. Attention: For patients with a weight lower than the ideal weight, the actual weight should be used to calculate the dosage.

Therefore, for the placebo/saline group, if the IBW is 70kg, the patient will receive an initial infusion of 0.9% sodium chloride at 5.25ml over 10-20 minutes, followed by an infusion at 1.75-5.25ml/h.

3. Dose adjustment

Dose changes are not allowed in this study. If the supervising medical professional suspects acute systemic local anesthetic toxicity symptoms, the infusion must be stopped and not continued. In this case, supportive treatment and lipid rescue will be provided. The discussion on the possible adverse events caused by lidocaine toxicity is as follows. If the infusion is interrupted due to issues such as infusion pump failure, catheter failure, or accidental disconnection, the infusion can be restarted at the original rate and the event recorded.

4. Additional care and procedures

To reduce the possibility of confounding factors, general anesthesia should be maintained under a combination of intravenous and inhalation anesthesia. Postoperative care follows the unit's standard to enhance postoperative rehabilitation protocol. The pain control program will be consistent with the unit's standard procedure. However, during IMP infusion, simultaneous continuous infusion of other local anesthetic drugs (such as epidural or wound catheters) cannot be performed.

5. Postoperative analgesia management

To reduce the possibility of confounding factors, general

anesthesia should be maintained under a combination of intravenous and inhalation anesthesia. Postoperative care follows the unit's standard to enhance postoperative rehabilitation protocol. The pain control program will be consistent with the unit's standard procedure. However, during IMP infusion, simultaneous continuous infusion of other local anesthetic drugs (such as epidural or wound catheters) cannot be performed. After the surgery, all patients were uniformly treated with sufentanil 2ug/kg diluted to 100ml and pumped with 2ml/h for intravenous analgesia

6. Randomization

After obtaining consent, participants will be randomly assigned (1:1) to receive intravenous lidocaine or placebo using a minimization algorithm. The minimum criteria include age (<45 years, 45-65 years, 65-80 years), gender, trial center.

6. Observation project

Main outcome measure

Assess the reoccurrence time of lung cancer patients within 36 months from the date of surgery.

Secondary outcome measure

1. Disease free survival (DFS)
2. Objective remission rate of patients' diseases
3. Health related Quality of Life Questionnaire EQ-5D-5L
4. Cancer specific quality of life measured using the Functional

Assessment of Cancer Therapy (FACT-L) questionnaire.

Other observation indicators

1. The total length of hospital stay, including readmission, is 36 months.
2. Changes in pro-inflammatory cytokine levels (IL-6, TNG - α) from baseline on the third day after treatment and upon discharge.

On the 1st and 3rd day after treatment and at discharge, changes in reticular fiber dissolution markers (matrix metalloproteinases MMP-9, MMP-2) from baseline were observed.

3. Perioperative nausea, vomiting, delirium, pain control, and incidence of cardiovascular accidents 6 and 12 months after treatment completion.

7. Efficacy evaluation criteria

Follow up chest CT scans at 6, 12, 18, 24, and 36 months after surgery were conducted to evaluate whether lung cancer patients had cancer reoccurrence and the time of reoccurrence within 36 months from the date of surgery. And evaluate the cancer specific quality of life using the lung cancer treatment function assessment questionnaire for patients. The shortened recurrence time and improved specific quality of life indicate therapeutic efficacy.

8. Observation of adverse events

Lidocaine can inhibit cancer cell proliferation at doses that have minimal impact on normal cells. The infusion dose and duration selected

in this study are within the recommended range of the latest international consensus statement on the safe use of intravenous lidocaine infusion. Lidocaine should be administered intravenously at an initial dose of no more than 1.5mg/kg of ideal body weight, with an initial infusion time of at least 10 minutes. During the maintenance period, the infusion rate of 1.5mg/kg/h should not exceed 24 hours, and the maximum infusion rate should not exceed 120mg/h. The above medication should be calculated based on ideal body weight. If the actual body weight is lower than the ideal body weight, it should be calculated based on the actual body weight. When toxicity occurs, according to the guidelines of the British and Irish Society of Anesthesiologists, lidocaine infusion can be temporarily suspended and treatment can be carried out using readily available 20% intravenous lipids in the operating room and intensive care unit.

9. Quality Control and Quality Assurance in Research

Strictly follow relevant SOPs during the clinical research process, conduct unified training before the implementation of the study, and monitor IMP/placebo infusion as part of the standard care for patients. Due to the infusion of IMP/placebo from the start of surgery until 12 hours after returning to the ward, all participants were hospitalized during the infusion period. The infusion rate table will be provided to the research team to minimize user errors during administration. The data

will be collected at the hospital during routine hospital appointments and postoperative recovery periods. We will strive to collect outcome data from all randomly assigned participants, regardless of whether they received IV lidocaine/placebo. Communicate with the surgeon and strictly follow the diagnosis and treatment plan according to the protocol. Strictly develop a follow-up plan form. The data is recorded using Redcap software.

10. Statistics process

Statistics will be recorded and managed using Redcap data, and analyzed using SPSS21 software. The analysis will be conducted according to the intention to treat principle. The statistical analysis plan for this study includes summarizing baseline data, conducting primary outcome analysis using time to event analysis, and conducting additional survival analysis. Baseline variables such as age group, gender, comorbidities, ASA classification, cancer stage, cancer TNM classification, pathological type, neoadjuvant targeted therapy, radiotherapy, and chemotherapy will be summarized using appropriate descriptive statistical methods, using mean and standard deviation or median and quartile range (depending on the applicability of continuous variables). The categorical variables will be summarized using the frequency and percentage of participants in each category. Researchers will use EDC to fill out CRF. The data will be stored on a secure server.

The source documents of CRF report information will be archived in the center and available for monitoring, IRB/IEC review, and regulatory inspection as needed. According to applicable regulations, researchers must retain all research records/documents.

The main outcome is defined as the time of cancer reoccurrence within 36 months after surgery in patients with stage I and II lung cancer. Multiple Cox regression models will be used to analyze the main results and adjust the truncated data. The truncated data includes participants who have not experienced recurrence or death within 36 months, as well as those who have been lost to follow-up or withdrawn from the study.

The risk ratio will be estimated by comparing the risk rates of the placebo group and the lidocaine group, taking into account the truncated data of the participants and adjusting for covariates. In addition, Kaplan Meier plots will be used to visualize and compare survival distributions, while Log rank tests will evaluate the differences between the two groups.

We will use the study drug allocation ($x=0$ placebo, $x=1$ lidocaine) as the independent variable, the time of cancer recurrence or death as the dependent variable, and age group (<45, 45-65, 65-80), gender, number of comorbidities, ASA classification, cancer staging, neoadjuvant radiotherapy, and chemotherapy as adjusted covariates.

Clean the experimental data and construct an analysis dataset suitable for statistical analysis. Data quality control is achieved through the accuracy

(numerical range), reasonableness (whether the category is reasonable), and handling of missing data (by checking and supplementing missing data). Then conduct statistical analysis. Missing data will be compensated through multiple imputation and pattern mixing methods to explore the robustness of treatment effect estimation. We will explore the reasons for missing data, such as loss to follow-up or withdrawal, and report them. We will seek clarification of missing data through routine data collection with the clinical team. Resolve data queries before analysis.

11、 Ethics in Clinical Research

Clinical research will follow relevant regulations such as the Helsinki Declaration of the World Medical Assembly. The clinical study will only be conducted after the ethics committee approves the trial protocol before the start of the research. Before each participant is enrolled in this study, the researcher is responsible for fully and comprehensively introducing the purpose, procedures, and potential risks of this study to the participant or their representative, and signing a written informed consent form. The participant should be informed of their right to withdraw from this study at any time, and the informed consent form should be kept as a clinical research document for future reference. During the research process, the personal privacy and data confidentiality of the subjects will be protected.

Research time

January 2026 December 2026: Project initiation, completion of data

collection for 400 patients

January 2027 December 2027: Complete data collection and mid-term analysis for 600 patients

January 2028 to October 2028: Complete data collection for 400 patients

October 2028 to December 2028: Data organization and statistical analysis. Complete the paper writing and submit the SCI paper as soon as possible.

Reference

1. 蔡林, 朱称心, 张兴龙, 房怡, 杨海燕, 郭兰伟: 全球肺癌流行数据解读. 中华流行病学杂志 2024, 45(04):585-590.
3. Ben-Eliyahu S, Golan T: Harnessing the Perioperative Period to Improve Long-term Cancer Outcomes. JNCI: Journal of the National Cancer Institute 2018, 110(10):1137-1138.
4. Wall TP, Buggy DJ: Perioperative Intravenous Lidocaine and Metastatic Cancer Recurrence - A Narrative Review. Frontiers in Oncology 2021, 11.

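### Table 1 lets maintenance lidocaine run from 0.5 mg/kg/h, half the 1 mg/kg/h minimum set in the dosing text

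*Protocol*

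**What the plan says.** The strength of the study drug is fixed in section 1 of Research methods (Intervention measures): "2% lidocaine hydrochloride injection for infusion, prepared as a 50mL syringe". Two per cent is 20 mg/mL.

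Section 2 (Dose plan) then gives the maintenance rate in three forms:

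- **Text.** After a 1.5 mg/kg bolus, the drug is "then continuously infused at 1-1.5 mg/kg/h until 12 hours after returning to the ward", "with a maximum rate of 120 mg/h".
- **Table 1 heading.** "IBW (Kg) initial dose (1.5 mg/kg) infusion rate (1.5 mg/kg/h)", a single rate.
- **Table 1 rows.** Ranges in mL/h by ideal body weight (IBW), from "40 3ml (10-20min) 1-3ml/h" at the bottom to "80 and above 6 ml (20 minutes) 2-6 ml/h" at the top.

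The worked saline example for a 70 kg patient has the bolus "followed by an infusion at 1.75-5.25ml/h", the same as the table's 70 kg row. Placebo is to run at the same rate as active drug.

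Section 8 (Observation of adverse events) mentions maintenance only as a ceiling: "the infusion rate of 1.5mg/kg/h should not exceed 24 hours", again with the 120 mg/h limit. Section 9 (Quality Control and Quality Assurance in Research) says the team will receive an infusion rate table to reduce administration errors.

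**The concern.** The lower mL/h figure in each row is one third of the upper figure. A range of 1 to 1.5 mg/kg/h would make it two thirds. The table therefore seems to encode a different minimum from the sentence it illustrates.

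The maintenance rate defines the experimental intervention, and pumps are set in mL/h, so the table is what staff are likely to use.

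- **If the text is right**, a patient can receive half the intended minimum while fully complying with Table 1.
- **If the table is right**, a rate from 0.5 to just under 1 mg/kg/h is outside the text.

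Either way, adherence to the assigned dose cannot be judged in that band, and centres may dose differently. Section 3 (Dose adjustment) allows no dose changes and has an interrupted infusion resume at its previous rate, so a low starting rate has no stated route to correction. The primary analysis is by intention to treat. If any benefit depends on exposure, dilution from low rates stays in the estimate.

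**Working it through.** **Inputs.** Concentration 20 mg/mL (section 1). Text range 1 to 1.5 mg/kg/h, cap 120 mg/h, and the Table 1 rows (section 2).

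**Formulas.**
- Table to dose: mg/kg/h = mL/h × 20 / IBW
- Text to pump rate: mL/h = IBW / 20 up to min(1.5 × IBW, 120) / 20
- Bolus: mL = 1.5 × IBW / 20

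**What reproduces.** The bolus formula gives 3, 3.75, 4.5, 5.25 and 6 mL at 40, 50, 60, 70 and 80 kg, exactly as in Table 1. The table's upper limits are exactly 1.5 mg/kg/h in each of these rows and reach 120 mg/h at 80 kg.

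**What does not.** The lower limits:

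| IBW (kg) | Table 1 (mL/h) | In mg/h | In mg/kg/h | Text range (mL/h) |
|---|---|---|---|---|
| 40 | 1-3 | 20-60 | 0.5-1.5 | 2-3 |
| 50 | 1.25-3.75 | 25-75 | 0.5-1.5 | 2.5-3.75 |
| 60 | 1.5-4.5 | 30-90 | 0.5-1.5 | 3-4.5 |
| 70 | 1.75-5.25 | 35-105 | 0.5-1.5 | 3.5-5.25 |
| 80 | 2-6 | 40-120 | 0.5-1.5 | 4-6 |
| 90 (top row) | 2-6 | 40-120 | 0.44-1.33 | 4.5-6 |
| 100 (top row) | 2-6 | 40-120 | 0.40-1.20 | 5-6 |

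The lower limit is half the text's at every listed weight. In the open-ended top row the factor grows to 4.5/2 = 2.25 at 90 kg and 5/2 = 2.5 at 100 kg.

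**Could another concentration explain it?** Taking the 40 kg row:

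| Concentration | Bolus (mg/kg) | Lower limit (mg/kg/h) | Upper limit (mg/kg/h) |
|---|---|---|---|
| 10 mg/mL | 0.75 | 0.25 | 0.75 |
| 20 mg/mL | 1.5 | 0.5 | 1.5 |
| 40 mg/mL | 3 | 1 | 3 |

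Only 20 mg/mL fits the bolus and the upper limit. The 40 mg/mL strength that would rescue the lower limit doubles the other two.

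**Could it be a table-reading fault?** All five rows show the same 1:3 ratio, and the saline example repeats 1.75 mL/h in running prose. That makes it implausible.

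**Effect on total dose at 70 kg.** The bolus is 1.5 × 70 = 105 mg. With T hours of maintenance, the total is 105 + 35T at the table minimum and 105 + 70T at the text minimum.

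| T (h) | Table minimum (mg) | Text minimum (mg) | Ratio |
|---|---|---|---|
| 12 (ward period only) | 525 | 945 | 0.556 |
| 14 | 595 | 1085 | 0.548 |
| 16 | 665 | 1225 | 0.543 |

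The time from induction to the ward is not stated. The last two rows assume 2 and 4 hours at the maintenance rate.

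**The case against.** The mismatch itself cannot be disputed; its weight can.

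- **No safety limit is breached.** Upper limits and cap agree, placebo is rate-matched so blinding is untouched, and sample size is unaffected. All of this stands.
- **The text should govern.** It is the directive sentence, the table is presented as an example, and 0.5 mg/kg/h is written nowhere. That is a reasonable reading, but the protocol has no precedence rule, the table applies its lower limit consistently, and section 8 gives only ceilings. Even if the text governs, the table still needs correcting.
- **The heading is only loose labelling.** It can be read as the rate behind the upper limits, which it matches. Fair, but it should be corrected in the same edit.
- **The totals are worst case.** They compare minimum with minimum for the whole infusion, and nothing shows staff would choose the bottom of the range. True. The text alone already allows a 1.5-fold spread with no rule for choosing within it; the table widens that to threefold.
- **Weights above 80 kg are uncommon.** Under the protocol's Broca formula, an IBW of 90 kg needs a man of 190 cm or a woman of 195 cm, whose actual weight is at least that. The 2.25 and 2.5 factors are therefore marginal. The same row does fix the bolus at 6 mL, which is 120/90 = 1.33 mg/kg at 90 kg against 1.5 mg/kg in the text, so agreement on the bolus holds only at the listed weights.
- **The rate table for staff is not shown.** Carry-over of the error depends on its being built from Table 1.

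**Conclusion.** The concern holds. The protocol gives two minimum maintenance rates for the study drug, 1 mg/kg/h in the text and 0.5 mg/kg/h in the pump rates, and a heading that matches neither range. The factor is two at every listed weight. This follows by unit conversion from figures in the document and needs no assumption beyond 2% meaning 20 mg/mL.

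The total-dose ratio of 56% at 70 kg covers the bolus and 12 ward hours at the respective minimum rates. The 54-55% figures also assume 2 to 4 hours of maintenance before the ward. These ratios bound the possible shortfall and do not predict average exposure. The document does not settle which minimum was meant.

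It must be corrected before dosing starts, because it concerns the dose of the investigational drug in the section staff work from.

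A secondary wording point does not affect this conclusion. On suspected toxicity, section 3 requires the infusion to stop for good, while section 8, citing a guideline, speaks of a temporary pause. Nothing expressly permits a restart after toxicity.

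**What to change.** State one maintenance range, chosen by the clinical team, and make the text, table heading, mL/h column and saline example agree before any rate table is issued.

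- **If 1 to 1.5 mg/kg/h is intended:** change the ranges to 2-3, 2.5-3.75, 3-4.5, 3.5-5.25 and 4-6 mL/h at 40, 50, 60, 70 and 80 kg. Above 80 kg, use a lower limit of 1 mg/kg/h (IBW/20 mL/h) with the 6 mL/h cap. Change the saline example to 3.5-5.25 mL/h and the heading to 1-1.5 mg/kg/h.
- **If 0.5 to 1.5 mg/kg/h is intended:** correct the dosing sentence and the heading, and give a weight-based lower limit above 80 kg.

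In either case, say whether the bolus is meant to be capped at 6 mL above 80 kg. Align the toxicity sentence in section 8 with the stop-and-do-not-restart rule in section 3.

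The cost is a few lines of text. Sample size, randomization and follow-up do not change.

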Cancer staging is indeed associated with recurrence, especially when cancer cells migrate from the primary site. Stage I ground glass nodules, even if the pathological type is invasive adenocarcinoma and larger than 3cm, still have a 5-year 100% survival rate. Stage III and IV lung cancer, due to the invasive spread of cancer, surgery is usually not for cure, but mainly for symptom relief, and lidocaine is unlikely to provide benefits. Stage I solid nodular lung cancer involves vascular and pleural invasion, while stage II involves vascular and lymphatic system invasion, requiring extensive surgical resection [12]. These patients may benefit the most from lidocaine and will be the main target of this study. We will recruit patients with all cancer stages to understand potential differences in

response to lidocaine treatment.

Lidocaine has an inhibitory effect on tumor cells, which is mostly based on animal studies, and toxic doses are often used in animal studies. There are few high-quality studies in clinical practice. This study aims to explore whether lidocaine infusion at a safe dose can bring the value of prolonging survival for lung cancer patients after surgery, which is of great significance.

Research objective

1. Main objective: To evaluate the effect of perioperative lidocaine infusion on postoperative reoccurrence and metastasis in patients with non-small cell lung cancer.
2. Secondary objective: To explore the value of perioperative lidocaine infusion in prolonging the survival of patients with non-small cell lung cancer

Research design types, principles, and experimental procedures

1. Research Design

This is a 1:1 parallel double-blind (patient and data collector blinded, prepared by anesthesia nurses and administered by anesthesiologists) randomized controlled trial comparing the efficacy of intravenous infusion of lidocaine versus placebo/saline during minimally invasive (thoracoscopic or robotic) surgery in lung cancer patients.

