1.1 Sample size calculation

For the time to event outcome, use the median reoccurrence time of similar populations in the literature to estimate the hazard ratio (HR). The median reoccurrence time described in the literature is 18 months. If we do not want to miss the 6-month improvement in event time in the treatment group, then HR estimates the risk ratio of reoccurrence time at 18 months in the control group and 24 months in the treatment group.

Risk ratio=(risk rate of treatment group)/(risk rate of control group)

Risk rate=1/(median recurrence time)

Therefore, the risk ratio can be estimated as: Risk ratio=(1/24)/(1/18)=18/24=0.75

The estimated risk ratio is 0.75, which represents a 25% reduction in risk effect for the treatment group compared to the control group. The sample size is based on the parallel design of the superiority program, survival endpoint, 90% efficacy, 0.05 significance level, bilateral significance level, HR 0.75. Using PASS11 software, it is estimated that each group requires 635 cases, and an increase of 10% would result in 700 cases per group. Therefore, the planned total sample size is 1400 patients with lung cancer.

2、 Case selection

In this experiment, qualified participants will be recruited from each center, as the annual number of lung surgeries in each center reaches around 8000 cases.

Inclusion Criteria

1. Age range: 18-80 years old.
2. Electively undergo minimally invasive (thoracoscopic or robotic) surgery for clinical stage I and II lung cancer.
3. Willing and capable of providing consent.

Exclusion criteria

1. Palliative surgery without intention of cure.

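### Clinical stage, which the protocol links to recurrence, is left out of the minimisation factors, and the additional log-rank test is not stated to be stratified by it

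*Protocol*

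**What the plan says.** On allocation, section 6 (Randomization) says that "participants will be randomly assigned (1:1) to receive intravenous lidocaine or placebo using a minimization algorithm", and then: "The minimum criteria include age (<45 years, 45-65 years, 65-80 years), gender, trial center". Stage is not among these factors.

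On stage, the background paragraph before the research objectives says "Cancer staging is indeed associated with recurrence, especially when cancer cells migrate from the primary site". Inclusion criterion 2 reads "Electively undergo minimally invasive (thoracoscopic or robotic) surgery for clinical stage I and II lung cancer", so each patient's clinical stage is on record before randomisation and takes two values.

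On analysis, section 10 (Statistics process) says "Multiple Cox regression models will be used to analyze the main results and adjust the truncated data". Its list of adjusted covariates includes cancer staging. Kaplan-Meier plots are then added, "while Log rank tests will evaluate the differences between the two groups". No stratification of that test is stated.

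**The concern.** Minimisation is normally spent on the baseline factors expected to matter most for the outcome. Stage is the factor that this protocol itself ties to recurrence, and it is available at the time of allocation. Leaving it out means that the arms can differ in stage by chance. A log-rank test that ignores stage then carries that difference. Even with perfectly balanced arms it loses some power, because it pools patients with different baseline hazards.

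At stake is the agreement between two results that will be reported side by side. One is a Cox hazard ratio adjusted for stage. The other is a log-rank p-value with Kaplan-Meier curves that are not adjusted. The allocation part cannot be repaired once patients are randomised. The test can be changed at any time before the data are unblinded.

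**Working it through.** **The plan's own figure.** The protocol gives no figure for stage balance. Its sample size is needed only to set the event proportion.
- Events for HR 0.75, two-sided 0.05 and 90% power (Schoenfeld): 4 × (1.960 + 1.282)² / (ln 0.75)² = 508.
- The stated 635 per group follows if 40% of patients have an event: 508 / 0.40 = 1270 = 2 × 635. The protocol does not state this 40%.
- The stated medians of 18 and 24 months, with exponential times and 36 months of follow-up, would give 69.8% instead, and 508 / 0.698 / 2 = 364 per group. The 40% is therefore an assumption here.

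**Inputs not in the protocol (assumed).** Stage II share 10-50%; hazard ratio of stage II to stage I 2-3; about 40% events.

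**Chance imbalance.** With 700 per arm and allocation that ignores stage, the SD of the between-arm difference in stage II share q is √(2q(1−q)/700).
- q = 0.10: SD 1.60 points, 95% limit ±3.1 points.
- q = 0.30: SD 2.45 points, 95% limit ±4.8 points.
- q = 0.50: SD 2.67 points, 95% limit ±5.2 points.

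If stage is correlated with age, gender or centre, the existing factors give some indirect balance and these limits are somewhat too wide.

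**Effect on an unadjusted hazard ratio.** Approximate shift in log HR at the 95% limit = limit × ln(stage HR).
- q = 0.10, stage HR 2: 0.022, so 0.75 becomes 0.734 to 0.767.
- q = 0.30, stage HR 2: 0.033, so 0.725 to 0.775.
- q = 0.50, stage HR 3: 0.058, so 0.708 to 0.794.

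The standard error of the log HR with 508 events is 2/√508 = 0.089. These extremes are thus about a quarter (0.022/0.089) to two thirds (0.058/0.089) of one standard error.

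**Simulation of the log-rank test.** 4000 runs per setting, N = 1270, 30% stage II, 36 months, true HR 0.75. The realised event proportion was 39.0% (stage HR 2) and 38.2% (stage HR 3).

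| Stage HR | Allocation | Plain log-rank power | Stratified log-rank power |
|---|---|---|---|
| 2 | stage not balanced | 0.875 | 0.887 |
| 2 | stage balanced | 0.881 | 0.895 |
| 3 | stage not balanced | 0.838 | 0.880 |
| 3 | stage balanced | 0.852 | 0.885 |

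Simulation error on each power is about ±1 point (1.96 × √(0.88 × 0.12 / 4000)). As a check, the Schoenfeld power for the realised events is Φ(0.2877 × √495 / 2 − 1.96) = 0.89 at stage HR 2, and 0.89 with 485 events at stage HR 3. The stratified test reaches this and the plain test falls short.

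Balancing stage alone gains 0.6 points (stage HR 2) or 1.4 points (stage HR 3), no more than simulation error can explain. Stratifying under the same allocation gains 1.2 to 1.4 points at stage HR 2 and 3.3 to 4.2 points at stage HR 3.

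**Type I error** (true HR 1, simulation error about ±0.7 points). The plain log-rank test without stage balance rejects in 4.9% (stage HR 2) and 4.6% (stage HR 3) of runs. With stage balanced but the test left plain, it rejects in 4.6% and 4.0%. Balancing on stage without stratifying by it therefore tends to make the test slightly conservative, so the two changes belong together.

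**The case against.** The strongest reply is that the plan already handles stage where it matters. The main analysis is a Cox model with cancer staging as a covariate, and the log-rank test is supplementary. Minimising on some factors and adjusting for others is an accepted design. This stands, and it limits the point to the log-rank test and the survival curves.

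It is also true that chance imbalance is not bias. Randomisation keeps the plain test at its level, the shifts above are 95% extremes, and they are small against the standard error. This stands too.

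Two stronger readings are tempting, and the documents support neither.
- A reader might infer that the primary result is exposed to stage imbalance. It is not, because section 10 adjusts for stage. That section does not say whether clinical or pathological stage is meant, but either would absorb most of an imbalance.
- A reader might infer from "We will recruit patients with all cancer stages to understand potential differences in" response that a stage-by-treatment term is missing. Response by stage is not a listed objective or outcome, and a subgroup analysis is commonly left to the statistical analysis plan, which is not at hand. An interaction test would also be weak: with 508 events, 20-50% of them in stage II, power for a ratio of hazard ratios of 0.75 is only 25-37%.

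Finally, the background's contrast in expected benefit is not stage I against stage II. It groups solid stage I nodules with stage II and sets ground-glass stage I apart. A two-level stage factor does not capture that contrast. The case for it rests only on the stated link between stage and recurrence.

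The objection does not answer why the one factor tied to recurrence, known in advance, is left out of the allocation at almost no saving.

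**Conclusion.** The point holds as a modest design improvement. It is not an error that threatens the primary analysis. Stage is omitted from the minimisation, and the log-rank test is not stated to be stratified by it. The consequence is about 84-88% power for the plain log-rank test against 88-90% for the stratified one, and some room for the log-rank and Cox results to disagree. Most of the gain comes from stratifying the test. Balance on stage by itself adds little measurable power, but it makes the unadjusted curves easier to read and cannot be added later.

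The size rests on assumed values: 30% stage II, stage HR 2-3 and about 40% events. With a weaker stage effect the gain shrinks. With the roughly 70% events implied by the stated medians, there would be about 0.698 × 1270 = 886 events. The reference power would then be Φ(0.2877 × √886 / 2 − 1.96), about 99%, and the loss in power points cannot be read from these runs.

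**What to change.** - In section 6, add clinical stage (I, II) as a fourth minimisation factor before enrolment starts. The protocol schedules its first 400 patients for 2026.
- In section 10, state that the log-rank test is stratified by clinical stage as recorded before randomisation.

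The sample size does not change, and no new data are needed because eligibility already requires clinical stage. The cost is one more factor in the allocation system, a slightly more complex algorithm and one changed line in the analysis section. If enrolment has already begun, the stratified test can still be adopted, but patients already randomised cannot be rebalanced.
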